## Vibration Impact on Tremor

### STUDY DESIGN:

We will perform a two-group, randomized, longitudinal study exploring the feasibility and impact of the RM Band vibration device on tremor of participants who suffer from Parkinson's disease (PD). This study will be a single session study with participants randomly assigned to one of two dose levels. PD patients will be recruited and randomized into either Group A (low dose) or Group B (high dose). Target enrollment for Group A and B is 15 participants each.

### STUDY VISIT PROCEDURE:

We will prescreen volunteers by phone or in the clinic for eligibility criteria (we are requesting partial waiver for recruiting purposes only). We will be obtaining names, contact information, and diagnosis from the registry to identify potential participants and reach out to them to determine if they are interested in participating. A member of the Parkinson Movement Disorder Center (PMDC) research registry staff shall pre-screen the registry for ID possible participants and will transmit the contact information to the staff of this study. Our study staff will contact the volunteer, explain the study, and determine if they wish to be scheduled for a screening visit. Informed consent will be obtained at that screening visit prior to any further assessments. After the informed consent is signed, the Mini Mental State Exam (MMSE) will be administered by the study coordinator to determine final eligibility to the study. Individuals with MMSE <24 will be excluded from the study.

Before study intervention start, we will confirm that the participant is in the "on" state, defined as when their medication is working, per confirmation from subject. If the participant is due to take their Parkinson's medications, they will be asked to take them, and then the study will begin approximately 30 minutes later to allow the medication a chance to work. If the participant confirms that they are not in their "on" state and they are not due to take their medication, we will wait an additional 30 minutes and if the participant still is not in the "on" state, we will reschedule the visit. If the participant confirms their medications are working the study will begin.

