### DATA COLLECTION:

Data will be collected at baseline (prior to vibration start), during treatment (after 5 minutes of vibration start and with vibration still turned on), and after vibration is stopped to assess the duration of effect. Vibration stimulation will last a total of 20 minutes.

Baseline data includes: (1) demographics (date of birth, sex); (2) disease descriptors (date of Parkinson's diagnosis, medication list, medical history, tremor history, and Movement Disorder Society Unified Parkinson Disease Rating Scale (MDS UPDRS) parts II-IV to assess the total burden of motor PD symptoms as well as their impact on activities of daily living for the prior two weeks; and (3) Tremor Rating Scale.

Estimated time to complete is 30 minutes. Demographics and disease descriptors will be obtained directly from patient, confirmation of diagnosis will be confirmed from medical records.

During treatment and post treatment data collection includes: (1) MDS UPDRS – part III only (motor assessment), and (2) Tremor Rating Scale. The time to complete these two assessments is estimated to be 15 minutes.

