### MEASUREMENTS:

The MDS UPDRS and the Tremor Rating Scale will be administered by the research coordinator under the supervision of the medically responsible PI or designee and will be videotaped, de-identified, and later evaluated by the PI (blinded to the participant's vibration frequency assignment) who will score the performance tests.

1) Movement Disorder Society - Unified Parkinson Disease Rating Scale (MDS UPDRS) - parts II-IV (Goetz, Tilley, Shaftman, Stebbins, Fahn, Martinez-Martin .... & LaPelle, 2008). All items are rated using a scale of 0 = normal to 4 = severe. Only Part III (Motor evaluation) will be repeated during vibration and post intervention data collection times and will take approximately 5 minutes to complete.

2) Clinical Rating Scale for Tremor – ( Fahn, Tolosa, & Marin, 1988).

We will use Part A, items 1 – 14 for analysis of tremor over time. The range of score for these items is 0 – 56. All items are rated on a scale of 0 = normal to 4 = severely abnormal. Total time to complete the Scale for Tremor assessment is 10 minutes.

3) Objective measurement of tremor –

This device will allow us to objectively measure tremors of both the right and left arms (a device will be worn simultaneously on each wrist) of the Parkinson's disease patients. This is being used as an experimental outcome measure to gather more quantitative tremor data such as frequency and amplitude using compact accelerometers and gyroscopes cased within the small light weight watch-like device. The objective tremor measuring device will be worn and will be recording 5 minutes before vibration is turned on, throughout vibration treatment to assess impact of vibration on tremor, and for approximately five minutes post treatment data collection to assess for possible carry over effects.

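### For participants dosed at the visit, time since dose rises with pre/during/post and is not among the listed data, so medication drift of unknown size and sign can enter Aim 1's within-group contrasts

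*Combined protocol and SAP*

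**What the plan says.** All section names refer to the combined protocol and SAP.

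- **Medication state (Study Visit Procedure).** The rule opens "Before study intervention start, we will confirm that the participant is in the" 'on' state, by the participant's own report. Someone who is due a dose takes it, and "the study will begin approximately 30 minutes later to allow the medication a chance to work". The further 30-minute wait, with rescheduling if that fails, is written for people who are not 'on' and not due a dose. The paragraph closes: "If the participant confirms their medications are working the study will begin".
- **Baseline (Data Collection).** The section begins "Data will be collected at baseline (prior to vibration start" and does not mention the 'on' check. For the baseline block, "Estimated time to complete is 30 minutes". It covers demographics, disease descriptors including the MDS UPDRS, and then the Tremor Rating Scale. The medication information is part of "medication list, medical history, tremor history"; time of last dose is not listed.
- **Later ratings (Data Collection, Measurements).** 'During' ratings start 5 minutes into a 20-minute vibration period, and 'post' ratings follow when it stops. Part III "will take approximately 5 minutes to complete" and the tremor scale takes 10 minutes. A motion sensor on each wrist records from 5 minutes before vibration.
- **Arms (Study Design).** The study has "participants randomly assigned to one of two dose levels", 15 per group. Both receive vibration.
- **Analysis (Data Analysis Plan, Aim 1).** A mixed model tests the group effect and also each frequency's effect over pre, during and post, at alpha 0.05. Time since dose is not a named covariate.

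**The concern.** Aim 1 reads change from baseline within each group as the effect of vibration, and Sample Adequacy makes the within-group means at the three time points the main product of the pilot. For someone dosed at the visit, the baseline, during and post ratings also fall at three increasing times after a dose. The plan itself says that the dose needs time to work. 'On' is a yes/no self-report, so reaching it does not show that the effect has levelled off.

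With no unvibrated arm, change due to medication and change due to vibration are added together in these contrasts. A dose still building up would make the device look better; wearing-off would make it look worse. Either would carry into the means and variances used to plan the next study. Because the study is a single session, a dose time not written down on the day may be unrecoverable, and the question could then not be examined later even descriptively.

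**Working it through.** **1. The plan's own figure.** The 15 per group rests on a precision rule with a minimum of 12. The 95% CI half-width in SD units is t(0.975, n−1)/√n: 0.635 at n = 12 and 0.554 at n = 15. Adding the 12th participant narrows it by 5.4% and the 15th by 4.1%, which agrees with the rule as described. The present point does not affect the sample size.

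**2. Timeline for a participant dosed at the visit.** The inputs are the 30-minute wait (Study Visit Procedure), the 30-minute baseline block, 20-minute vibration and 'during' start at 5 minutes (Data Collection), and 5 + 10 = 15 minutes for Part III plus the tremor scale (Measurements). I assume no gaps and that baseline follows the wait. Times are minutes after the dose.

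| | Ratings last in block | Ratings first in block |
|---|---|---|
| Baseline block | 30–60 | 30–60 |
| Baseline ratings | 45–60 | 30–45 |
| Vibration | 60–80 | 60–80 |
| 'During' ratings | 65–80 | 65–80 |
| 'Post' ratings | 80–95 | 80–95 |
| Gap to 'during', start to start | 65 − 45 = 20 | 65 − 30 = 35 |
| Gap to 'post', start to start | 80 − 45 = 35 | 80 − 30 = 50 |

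If the block were instead done inside the wait, every entry would move 30 minutes earlier and the gaps would be unchanged. The sensors' pre-vibration recording is at 55–60, next to vibration, so it is less exposed.

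**3. Bias.** Let k of 15 participants be dosed and drift by d, in SDs of the change score, with no vibration effect. The bias in the group mean change is k × d / 15. Both k and d are assumptions. With d = 0.5 per 35 minutes and linear drift, the 20-minute gap gives 0.5 × 20/35 = 0.286. The bias is then 3 × 0.286/15 = 0.06 SD or 6 × 0.286/15 = 0.11 SD.

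**4. False positives.** These come from 400,000 simulated two-sided paired t tests, n = 15, SD 1 excluding drift, as an approximation to the mixed-model time contrast. Nominal is 5%.

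| k of 15 | d per 35 min | 20-minute gap: bias; rate | 35-minute gap: bias; rate |
|---|---|---|---|
| 3 | 0.5 | 0.06; 5.4% | 0.10; 6.0% |
| 6 | 0.5 | 0.11; 6.7% | 0.20; 10.0% |
| 3 | 1.0 | 0.11; 6.3% | 0.20; 8.6% |
| 6 | 1.0 | 0.23; 11.6% | 0.40; 22.8% |

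The 20-minute column is during-minus-pre with ratings last. The 35-minute column is during-minus-pre with ratings first. It also applies to post-minus-pre with ratings last, provided the drift stays linear that long.

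**5. Sign.** Wearing-off of 0.5 SD per 35 minutes in 6 of 15 gives −0.20 SD at the 35-minute gap and −0.11 SD at 20 minutes. Equal numbers with equal onset and wearing-off cancel in the mean.

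**6. Randomised comparison.** In 40,000 simulated trials with the same expected share dosed in both groups, the low-versus-high test of change rejected in 5.1% to 5.2%. It is not inflated.

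**7. Would excluding those dosed at the visit reveal the drift?** The half-width is 0.64 SD with 12 left and 0.77 SD with 9 (2.306/√9), against biases of 0.06 to 0.20 SD in the 0.5 SD cases. It would not. Wearing-off could also remain: if 3 of 9 drift by −0.5 SD, the bias is −3 × 0.5/9 = −0.17 SD.

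**The case against.** - **The 'on' check already covers baseline.** Read in order, Study Visit Procedure goes from consent to cognitive screen to 'on' check to the start of the study, and its closing sentence most naturally gates all data collection. A reader might infer that baseline is rated during the wait, before the dose works. The documents do not support that; they only leave the link between check and baseline unstated, because the check is tied to intervention start. This part is a wording point. It leaves open whether the dose is still taking effect after 'on' is reported.
- **The drift is hypothetical.** This is correct. Its size and direction are not in the documents, being due a dose does not mean being 'off', and dosing those who are due partly limits wearing-off. The figures above illustrate sensitivity and are not estimates.
- **The likelier order gives the smaller figures.** Data Collection lists the Tremor Rating Scale last. That is not a mandated sequence, but if followed it gives about 20 minutes to 'during' for that scale and slightly longer for Part III. The 35-minute column is therefore not the likeliest case for during-minus-pre.
- **There is a partial control.** Sensors are on both wrists and the band is on one arm. The other arm could reflect systemic medication change. However, no such analysis is planned, the rating scales are not covered, and the band goes on the worse arm, so the two sides are not equivalent.
- **This is an exploratory pilot.** That is true, and it keeps the matter modest. Within-group change over time is nevertheless what the pilot sets out to estimate.

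**Conclusion.** The concern holds in a limited form. For participants dosed at the visit, time since dose runs in step with the pre/during/post factor, it is not among the listed data, and no unvibrated arm shows what medication alone would do. Any drift therefore enters the within-group contrasts of Aim 1. On the assumptions of 3 to 6 of 15 dosed, linear drift of 0.5 SD per 35 minutes and ratings last, the during-minus-pre bias is about 0.06 to 0.11 SD and false positives are about 5% to 7%. Both are larger if the ratings come first, and for post-minus-pre.

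Two stronger conclusions are tempting and not supported. A reader might infer that the plan is tilted in favour of the device, but wearing-off would act the other way and nothing in the documents settles which prevails. A reader might also infer that the low-versus-high comparison is biased, but randomisation protects it on average. The point is worth acting on because the remedy costs almost nothing and the missing dose time may not be recoverable.

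**What to change.** 1. State in Study Visit Procedure that 'on' is confirmed immediately before the baseline Part III, tremor scale and sensor recordings, including after a dose taken at the visit, and that none of these is taken during the wait.
2. Do Part III and the tremor scale last in the baseline block. Compared with doing them first, this shortens the gap to 'during' from 35 to about 20 minutes and the gap to 'post' from 50 to 35.
3. Add clock-time fields for the last dose and for each rating.
4. Report within-group changes with time since dose shown descriptively. Where useful, set the sensor data from the unvibrated wrist beside those from the treated wrist as a partial within-person reference.

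I would not add an analysis excluding participants dosed at the visit as a test for drift; step 7 of the working shows that it is too imprecise.

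The cost is one clarified sentence, a fixed rating order, a few data fields and a slightly longer visit for some participants. Arms, sample size and medication are unchanged. These steps reduce the drift and make it visible; they do not fully separate medication from vibration, and wearing-off may remain.

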### DATA COLLECTION:

Data will be collected at baseline (prior to vibration start), during treatment (after 5 minutes of vibration start and with vibration still turned on), and after vibration is stopped to assess the duration of effect. Vibration stimulation will last a total of 20 minutes.

Baseline data includes: (1) demographics (date of birth, sex); (2) disease descriptors (date of Parkinson's diagnosis, medication list, medical history, tremor history, and Movement Disorder Society Unified Parkinson Disease Rating Scale (MDS UPDRS) parts II-IV to assess the total burden of motor PD symptoms as well as their impact on activities of daily living for the prior two weeks; and (3) Tremor Rating Scale.

Estimated time to complete is 30 minutes. Demographics and disease descriptors will be obtained directly from patient, confirmation of diagnosis will be confirmed from medical records.

During treatment and post treatment data collection includes: (1) MDS UPDRS – part III only (motor assessment), and (2) Tremor Rating Scale. The time to complete these two assessments is estimated to be 15 minutes.

## Vibration Impact on Tremor

During and after vibration study the participant will be asked qualitative questions about the stimulus and apparatus including: How are you feeling? Do you have any pain? What does the vibration sensation feel like? Is it tolerable? How does the arm band itself feel? Is it comfortable? Are you having any unexpected sensations in your arm or fingers? Anything else you would like to comment on? RESEARCH

### MEASUREMENTS:

The MDS UPDRS and the Tremor Rating Scale will be administered by the research coordinator under the supervision of the medically responsible PI or designee and will be videotaped, de-identified, and later evaluated by the PI (blinded to the participant's vibration frequency assignment) who will score the performance tests.

1) Movement Disorder Society - Unified Parkinson Disease Rating Scale (MDS UPDRS) - parts II-IV (Goetz, Tilley, Shaftman, Stebbins, Fahn, Martinez-Martin .... & LaPelle, 2008). All items are rated using a scale of 0 = normal to 4 = severe. Only Part III (Motor evaluation) will be repeated during vibration and post intervention data collection times and will take approximately 5 minutes to complete.

2) Clinical Rating Scale for Tremor – ( Fahn, Tolosa, & Marin, 1988).

We will use Part A, items 1 – 14 for analysis of tremor over time. The range of score for these items is 0 – 56. All items are rated on a scale of 0 = normal to 4 = severely abnormal. Total time to complete the Scale for Tremor assessment is 10 minutes.

3) Objective measurement of tremor –

This device will allow us to objectively measure tremors of both the right and left arms (a device will be worn simultaneously on each wrist) of the Parkinson's disease patients. This is being used as an experimental outcome measure to gather more quantitative tremor data such as frequency and amplitude using compact accelerometers and gyroscopes cased within the small light weight watch-like device. The objective tremor measuring device will be worn and will be recording 5 minutes before vibration is turned on, throughout vibration treatment to assess impact of vibration on tremor, and for approximately five minutes post treatment data collection to assess for possible carry over effects.

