### INTERVENTION:

The RM Band (Resonate Forward LLC) is a small, untethered device that is attached to a soft elastic arm band. Inside the band are small vibration motors that deliver vibration like that of a cell phone on vibration mode. Through the controller inside the small box we can “set” the amplitude and frequency of the vibration. The armband is placed on arm that is more effected by tremor (determined by investigator). If both arms are equally effected, then the participants dominant arm will be used. Once the RMBand is in place, the vibration will be set at the frequency dictated by randomized group assignment. The amplitude duty cycle will be set so that the participant can feel the vibration. If the participant cannot feel the vibration, we will note it and continue with the study. Data collection will follow based on above description.

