## Vibration Impact on Tremor

for continuous variables with skewed distributions. Because of the exploratory nature of this pilot intervention study, no adjustment for multiplicity is planned with alpha set at 0.05 for determining significance. The analysis plan for each aim will be discussed separately.

Aim 1: To determine the impact of vibration delivered by the RMBand on parkinsonian tremor pre (baseline), during, and post vibration intervention. It is anticipated that a linear mixed effects model (Brown & Prescott, 2006; Verbeke & Molenberg, 2000; Vonesh & Chinchilli, 1997) will be used to test the group effect (low frequency vs. high frequency) as well as testing the effect each frequency across time (pre, during and post). The general form of the mixed linear model is given by  $y = XB + ZU + e$ , where  $y$  is the observed data vector (e.g., stress),  $X$  is a known design matrix,  $B$  is a vector of unknown fixed effects,  $Z$  is a known design matrix,  $U$  is a vector of unknown random effects, and  $e$  is a vector of unknown random errors. This model will include random effect for participant (represented by  $ZU$  in the equation), and fixed effects for group and time (represented by  $XB$  in the equation). The model is flexible enough to model potential cofactors including demographic or disease descriptors. Modeling assumptions such as normality and homoscedasticity will be checked for each model. In the case of non-normal data, a transformation (such as a log-transformation) will be used to normalize the data. Analyses will be performed using SAS software, specifically PROC MIXED and JMP.

Aim 2: To evaluate the safety and tolerability of the RMBand vibration device applied to the arm of the person with Parkinson's disease tremor. Safety and tolerability of the RMBand will be ascertained by qualitative questions such as: How are you feeling? Do you have any pain? What does the vibration sensation feel like? Is it tolerable? How does the arm band itself feel? Is it comfortable? Are you having any unexpected sensations in your arm or fingers? Anything else you would like to comment on? Answers to these questions will be tabulated by group and across groups.

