### SAMPLE ADEQUACY:

The overarching goal of this pilot study is to obtain good estimates of means and variances of the three research measures (MDS UPDRS, Tremor Rating Scale & watch device) at pre, during and post vibration therapy change over time within each of the 2 groups. van Belle (2008) proposed that a minimum of 12 subjects is needed to calculate confidence intervals based on a t-statistic with n-1 degrees of freedom, based on the fact that confidence interval half-width decreases rapidly up to n=12, at which point the decrease is less dramatic. Thus, the proposed sample size of 15 subjects per group should be adequate to estimate means and variances to assess group differences and trends over time.

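### The video scorer is blinded to vibration frequency but not, as far as the plan states, to time point, so the pre/during/post change on the two rated scales is open to rater expectation

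*Combined protocol and SAP*

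**What the plan says.** Under Measurements, the coordinator administers the MDS UPDRS and the Tremor Rating Scale, supervised by the PI or a designee. The sessions "will be videotaped, de-identified, and later evaluated by the PI". The one blind stated for the PI concerns the "vibration frequency assignment) who will score the performance tests".

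Under Data Analysis Plan, Aim 1 uses a linear mixed model to "test the group effect (low frequency vs. high frequency) as well as testing the effect each frequency across time (pre, during and post"). Both arms receive vibration: "PD patients will be recruited and randomized into either Group A (low dose) or Group B (high dose"). No sham or unvibrated arm is described.

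Session content differs by time point. Data Collection puts MDS UPDRS Parts II to IV at baseline. Measurements says that only Part III "will be repeated during vibration and post intervention data collection times". The paragraph that follows Data Collection adds: "During and after vibration study the participant will be asked qualitative questions about the stimulus and apparatus".

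Sample Adequacy gives the pilot's goal, which is to "obtain good estimates of means and variances of the three research measures" at pre, during and post within each group.

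**The concern.** The plan accepts that the scorer needs a blind, but applies it to only one of the two contrasts in Aim 1. In the within-frequency test the condition being compared is the time point itself. A scorer who does not know the frequency but can tell a baseline clip from a during-vibration clip may expect improvement and score accordingly.

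De-identification removes who the participant is. It does not by itself remove when the clip was taken. If the baseline interview parts or the questions about the vibration are on the recordings, they give the time point away. The scorer may also have been present, since the PI is one of those who may supervise the session.

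At stake is the change in means on two of the three research measures, which is a large part of what the pilot is meant to deliver. A larger sample would not remove such a bias.

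**Working it through.** The plan states no figure on this point, so there is none to reproduce. The check has two parts: a comparison of the text, and an illustration of size on assumed inputs.

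**Which blind covers which contrast**

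| Aim 1 contrast on the rated scales | What the scorer must not know | Stated in the plan? |
|---|---|---|
| Low vs high frequency | Frequency assignment | Yes (Measurements) |
| Pre vs during vs post, within a frequency | Time point | No |

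No section mentions removal of time labels, shuffled clip order or masking of time point.

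**Illustration of size**

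Inputs from the documents: 15 per group (Study Design), alpha 0.05 and three time points (Data Analysis Plan). Inputs assumed: a two-sided test, no true effect, a constant rater shift *b* of 0.1 to 0.2 between-person SD from pre to during, and a within-person correlation *r* of 0.5 to 0.9.

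*Step 1, paired t-test in one group.* In between-person SD units, the SD of change is √(2(1 − r)). The noncentrality is b√15 / √(2(1 − r)), with 14 df. For b = 0.2 and r = 0.9 this is 0.2 × 3.873 / 0.447 = 1.732, and the rejection rate is 36.5%.

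*Step 2, closer to the planned model.* Take a random participant intercept with fixed group and time, plus a group-by-time term. The plan does not list that term; it is assumed here so that each frequency has its own time effect. Error df = 90 observations − 30 participants − 2 (time) − 2 (group by time) = 56. The noncentrality of the pre-versus-during contrast within one group is the same as in step 1.

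| Shift b | r | Paired t, 14 df | Model contrast, 56 df |
|---|---|---|---|
| 0.1 | 0.5 | 6.5% | 6.7% |
| 0.1 | 0.7 | 7.5% | 7.8% |
| 0.1 | 0.8 | 8.8% | 9.2% |
| 0.1 | 0.9 | 12.7% | 13.6% |
| 0.2 | 0.5 | 11.2% | 11.9% |
| 0.2 | 0.7 | 15.4% | 16.6% |
| 0.2 | 0.8 | 20.8% | 22.6% |
| 0.2 | 0.9 | 36.5% | 39.9% |

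Simulation of the model contrast (100,000 runs) gave 6.7% and 13.7% for b = 0.1 at r = 0.5 and 0.9, and 11.8% and 40.1% for b = 0.2. With no shift it gave 5.0% and 5.1%.

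*Step 3, sensitivity to the scale of the shift.* If 0.1 to 0.2 is read as SDs of the change, the noncentrality is b√15 = 0.387 to 0.775, and the paired t-test rejects in 6.5% to 11.2%.

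*Step 4, the randomized contrast.* A shift common to both groups drops out of the difference in change. In the same simulations the low-versus-high comparison stayed at 4.9% to 5.1%.

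*Step 5, in points.* On the 0 to 56 tremor score, with an assumed SD of 4 to 12, the shift runs from 0.1 × 4 = 0.4 to 0.2 × 12 = 2.4 points.

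**The case against.** The strongest reply is that the plan is silent, not wrong. It never says that the scorer will know the time point, and a short protocol may leave clip handling to operating procedures. The material to be scored over time, Part III and the Tremor Rating Scale, is the same at all three time points, and the questions about the vibration are not said to be filmed. This stands as a limit: the gap is an unstated safeguard, not evidence of bias. It does not close the point, because the plan does name the scorer's blind and that blind leaves out the time contrast.

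Second, the percentages come wholly from assumed inputs, and the top of the range needs a 0.2 SD shift together with a correlation of 0.9. An exploratory pilot is also about estimates more than tests. Both are fair. The percentages show only that a small shift can matter. In terms of estimates, a constant shift leaves variances alone and moves the change in means on two measures, while the wrist sensor is unaffected. But the plan labels the sensor experimental and gives it no precedence, and it does test the time effect at 0.05.

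Third, masking cannot be complete. Vibration may be visible or audible in the during clips, and without a sham group the participant's own expectation stays in the time effect. This stands too, so the benefit is partial. Masking pre against post remains feasible.

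Finally, the frequency blind holds only if the PI does not learn the assignment while supervising a session. That qualifies the protection of the low-versus-high test and is a further reason to tighten the scoring procedure.

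**Conclusion.** The concern holds. The stated blind covers the low-versus-high comparison but not the change across pre, during and post on MDS UPDRS Part III and the Tremor Rating Scale. The documents give neither the size of any rater shift nor the SDs and correlations needed to judge it. Under the assumptions shown, the effect on the within-group test runs from nearly none to large (6.5% to about 40% in place of 5%). The conclusion rests on the text and not on those figures. The randomized comparison of change is safe under a common shift, provided that the frequency blind holds. This should be corrected, with medium confidence that it matters in practice.

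**What to change.** Under Measurements, state that the performance-test clips are:

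- coded and stripped of time labels;
- trimmed to the items common to all three time points, with no Part II or IV interview and no questions about the vibration;
- scored in random order across participants and time points, by a PI blinded to time point as well as to vibration frequency.

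Add one line that the band is on the arm and looks the same in all three recordings. Intervention describes fitting the band and then says "Data collection will follow based on above description", which reads as if the band is on before baseline, but whether it is worn in the post recording is not stated. If any of this is already the procedure, it is enough to say so.

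The cost is small: coding, trimming and shuffling 30 × 3 = 90 recordings that are already planned for later scoring. At the plan's estimate of 15 minutes per repeated assessment, that is 90 × 15 / 60 = 22.5 hours of video to prepare. Random order across participants also means holding the scoring until enough sessions are complete. Sample size and visits do not change. What masking cannot remove, namely during clips unmasked by the vibration itself and participant expectation without a sham group, should be stated as a limitation of the time effect.
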